5.3 Vulnerable Subjects

Vulnerable subject populations will not be included in this study. The study will not enroll Children, pregnant women, fetuses, neonates, prisoners, or persons with decisional incapacity.

5.4 Strategies for Recruitment and Retention

This study will utilize EPIC to identify prospective subjects.

The privacy of prospective subjects will be protected during the identification process. All members of the research team will have access to EPIC. The research team will consist of study surgeons, investigators, treating physicians and research coordinators. Study staff members are experienced at consenting patients or prospective subjects for anesthesiology studies, and they include physicians as well as qualified designated team members. Eligible patients or prospective subjects will be assessed for capacity to give informed consent by a study team member. The study team does not anticipate any subjects will have questionable or impaired capacity. As such, judgment that prospective subjects have the capacity to consent to the research can ordinarily be made informally during routine interactions with the individual during the consent process as described in section 11.6 of the NYU SOM IRB Policy and Procedures document. Medical status/stability will be addressed by members of the research team. Eligible patients or prospective subjects will be invited to participate in the study. Data will be discarded at least 3 years after closing out or 5 years after final reporting, whichever is longer, by deleting from the network.

Any recruitment information sent by email will utilize Send Safe email.

To first screen for eligible subjects, participating study surgeons, investigators, treating physician will review their appointment, operating, and other schedules on EPIC to identify eligible patients or prospective subjects for study recruitment. Eligible patients are those described in Section 5.1: diagnoses with endometriosis, experiencing chronic pain, and scheduled or being scheduled for a robotic removal of endometriosis surgery. Research team members may also screen for eligible prospective subjects on all participating physicians' schedules on EPIC and will contact these prospective subjects on their behalf with permission of study surgeons, investigators, and/or treating physician. The subjects' data will be screened to see if they match the study's eligibility criteria. The research team members will search EPIC as many times as needed until all 30 eligible subjects are recruited. Once eligible subjects are identified, recruitment can either be in-person or over the phone.

1. Recruited in-person

A research team member will speak to the eligible subject during appointments at NYU Langone Gynecology locations including outpatient facilities and hospitals. The study surgeon may also talk to subjects about the study during their appointment and can refer subjects who are eligible. Surgeons may give potential participants the IRB-approved research flyer with key information document to introduce the study. Once a subject has been referred, a study team member will call the subject through the "recruitment and enrollment over the phone" strategies listed below. Should the potential subjects agree, the study team member will complete the informed consent process.

2. Recruitment and enrollment over the phone

a. The IRB-approved telephone script will be used to communicate the reason participants are being contacted. They will be asked if they are interested in participating in this specific study. Research team members will call prospective subjects or arrange a video conference session (WebEx only). The study team member will then ask pre-screening questions, and if deemed eligible, the study team member will explain the consent to the prospective subject and ask if the prospective subject has any questions before the prospective subject electronically signs. The study team will immediately destroy any information collected from subjects who are either determined to be ineligible or who are eligible but decide not to enroll in the study. If the prospective participant agrees, they will be sent a copy of the informed consent via REDCap. The prospective subject will remotely receive a link to the informed consent form, sign, and return informed consent document through REDCap.

May 2, 2022 Version: 1.23 Page 12

Once informed consent is given, the study team member will provide the prospective subjects with information regarding the next steps for participation. Consent may occur up to two months before surgery. Subjects will also be consented no less than 2 days before their surgery.

If a subject requests information regarding opting out of further recruitment for all research, subjects will be directed to contact [contact] or [name].

The inclusion and exclusion criteria in this study should not have a negative effect on the enrollment of the desired populations. Treatment will take place at the NYU Langone Health Tisch/Kimmel Hospital under the supervision of the PI. Prospective subjects will receive detailed information regarding this study; its investigational nature, required study procedures, alternative treatments, risks, and potential benefits of the study. They will also receive the informed consent document to read. All questions are answered by the PI and qualified research personnel.

Recruitment and consenting will take place in a private area such as exam room (if in person) or remotely (phone call and video conference call) to protect the patient or prospective subject's privacy.

We anticipate recruitment to take approximately 5 months.

5.5 Duration of Study Participation

Participant participation will last up to 84 days starting at enrollment. There are 6 visits in total, each visit lasting less than 1 hour.

5.6 Total Number of Participants and Sites

Target accrual for this study is 30 subjects. Recruitment will end when approximately 50 participants are enrolled. It is expected that approximately 50 participants will be enrolled in order to maintain 30 participants for the duration of the study. The sites include NYU Langone Health Tisch/Kimmel Hospital.

5.7 Participant Withdrawal or Termination

5.7.1 Reasons for Withdrawal or Termination

Participants are free to withdraw from participation in the study at any time upon request for any reason, and without repercussion. Participants who withdraw consent will be counseled that their withdrawal only affects uses and sharing of information after their written request to withdraw authorization has been received, and that their authorization may not be withdrawn for uses or disclosures that have previously made or need to be made to complete analyses or report data from the research. For the confidentiality of randomization, only the physician administering the study drug will know which group the subject(s) is/are in for both experimental and control group. All data and records generated during this study will be kept confidential in accordance with institutional policies and HIPAA on subject privacy. The study investigators will not use such data and records for any other purpose other than conducting the study. Privacy protection procedures are in place and good clinical practice guidelines will be followed throughout the study to minimize the risks associated with breach of confidentiality. This risk will be minimized by strict compliance with HIPAA procedures for securing PHI. Information that could be used to identify the subject will only be shared with researchers who have approval of the IRB.

The investigator and sponsor have the right to discontinue a subject from study treatment or withdraw a subject from the study at any time. If a subject is discontinued from the study at the discretion of a PI or other delegated individual, the reason for discontinuation procedures will be noted in the subject's research record.

An investigator may terminate participation in the study if, but are not limited to:

Subject withdrawal of consent at any time

May 2, 2022 Version: 1.23

Page 13

- Disease progression
- Intolerable toxicity
- Any medical condition that the investigator or sponsor determines may jeopardize the subject's safety if the subject continues treatment with the study drug
- The investigator or sponsor determines it is in the best interest of the subject
- Failure of the subject to adhere to protocol procedure requirements
- Study termination by sponsor
- Any clinical adverse event (AE), laboratory abnormality, or other medical condition or situation occurs such that continued participation in the study would not be in the best interest of the
- The participant meets an exclusion criterion (either newly developed or not previously recognized) before surgery that precludes further study participation.

Criteria for discontinuing study intervention includes but not limited to:

- Allergic reaction thought to be related to study drug
- Uncontrolled hypertension, hypotension, or arrhythmia thought to be related to study drug
- Severe psychomimetic side effects
- Medical events/logistical reasons not related to study therapy

Study physician will be responsible for determining whether study interventions will be discontinued, based on his or her clinical judgement. In the case of cardiovascular side effects, if such side effects persist despite treatment based on PACU clinician's decisions, study drug may be discontinued. The reason for the dose discontinuation should be documented.

Psychomimetic side effects will be monitored by study and PACU physicians. Such side effects may be treated with reassurance. If participants continue to complain of anxiety or dysphoria or are agitated, pharmacologic agents (such as benzodiazepines) may be administered based on clinical judgement of PACU clinicians. If psychomimetic side effects are felt to be severe, with severe hallucinations, delusions, or agitation, study drug will be discontinued.

Additionally, in the event of any discontinuation of study intervention, with consent, participants will continue with the completion of remaining study visits.

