5.7.2 Handling of Participant Withdrawals or Termination

Subjects, who choose to withdraw consent, can do so by notifying the treating physician, the Principal Investigator or research staff in writing or verbally. Any data remaining after formal withdrawal, will be destroyed/discarded per Institutional guidelines. Subject will be informed whether the data will be retained and analyzed up to the point of withdrawal. The study team will document the reason for discontinuation in the subjects' research record. Every effort will be made to undertake protocol-specified safety follow-up procedures to capture AEs, serious adverse events (SAEs), and unanticipated problems (UPs). If subjects withdraw or discontinue early replacement participants will be allowed.

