8.3 Time Period and Frequency for Event Assessment and Follow-Up

The occurrence of an AE or SAE may come to the attention of study personnel during study visits and interviews of a study participant presenting for medical care, or upon review by a study monitor. All AEs including local and systemic reactions not meeting the criteria for SAEs will be captured on the appropriate CRF. Information to be collected includes event description, time of onset, clinician's assessment of severity, relationship to study product (assessed only by those with the training and authority to make a diagnosis), and time of resolution/stabilization of the event. All AEs occurring while on study must be documented appropriately regardless of relationship. All AEs will be followed to adequate resolution.

Any medical condition that is present at the time that the participant is screened will be considered as baseline and not reported as an AE. However, if the study participant's condition deteriorates at any time during the study, it will be recorded as an AE. UPs will be recorded in the data collection system throughout the study.

Changes in the severity of an AE will be documented to allow an assessment of the duration of the event at each level of severity to be performed. AEs characterized as intermittent require documentation of onset and duration of each episode.

The PI will record all reportable events with start dates occurring any time after informed consent is obtained until 7 (for non-serious AEs) or 30 days (for SAEs) after the last day of study participation. At each study visit, the investigator will inquire about the occurrence of AE/SAEs since the last visit. Events will be followed for outcome information until resolution or stabilization.

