13.5 Participant and Data Confidentiality

Information about study subjects will be kept confidential and managed according to the requirements of the Health Insurance Portability and Accountability Act of 1996 (HIPAA). Those regulations require a signed subject authorization informing the subject of the following:

- What protected health information (PHI) will be collected from subjects in this study
- Who will have access to that information and why
- Who will use or disclose that information
- The rights of a research subject to revoke their authorization for use of their PHI.

In the event that a subject revokes authorization to collect or use PHI, the investigator, by regulation, retains the ability to use all information collected prior to the revocation of subject authorization. For subjects that have revoked authorization to collect or use PHI, attempts should be made to obtain permission to collect at least vital status (i.e., that the subject is alive) at the end of their scheduled study period.

Participant confidentiality is strictly held in trust by the participating investigators, their staff, and the sponsor(s) and their agents. Therefore, the study protocol, documentation, data, and all other information generated will be held in strict confidence. No information concerning the study or the data will be released to any unauthorized third party without prior written approval of the sponsor.

The study monitor, other authorized representatives of the sponsor, representatives of the IRB or pharmaceutical company supplying study product may inspect all documents and records required to be maintained by the investigator, including but not limited to, medical records (office, clinic, or hospital) and pharmacy records for the participants in this study. The clinical study site will permit access to such records.

May 2, 2022 Version: 1.23

2, 2022 Page 29

The study participant's contact information will be securely stored at each clinical site for internal use during the study. At the end of the study, all records will continue to be kept in a secure location for as long a period as dictated by local IRB and Institutional regulations.

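### Section 5.7.1 lets the investigator end follow-up, not only the single POD 0 infusion, so terminations that follow returning pain can attenuate the POD 27 to POD 83 comparison

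*Combined protocol and SAP*

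**What the plan says.** Section 5.7.1 introduces its reasons for ending participation with "An investigator may terminate participation in the study if, but are not limited to", so the list is open-ended and concerns the study, not only the drug. Among the reasons are "Disease progression", which is not defined anywhere, and "Failure of the subject to adhere to protocol procedure requirements". Another begins "Any clinical adverse event (AE), laboratory abnormality, or other medical condition or situation occurs such that continued participation in the study would not be in" and goes on to refer to the participant's best interest.

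Sections 6.1.5 and 6.1.7 give the drug once, in the PACU on POD 0, over about 30 minutes. The primary VAS is taken at enrollment and POD 1, 27, 55 and 83 (sections 4.2.1 and 10.3.2).

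Two provisions keep women in follow-up. At the end of section 5.7.1, "in the event of any discontinuation of study intervention, with consent, participants will continue with the completion of remaining study visits". Section 7.2.5 tells participants that they may ask to stop the drug and stay in the study. Section 5.7.2 promises safety follow-up after withdrawal and allows replacement. On data it says "Any data remaining after formal withdrawal, will be destroyed/discarded per Institutional guidelines", while section 13.5 says that the investigator "retains the ability to use all information collected prior to the revocation of subject authorization".

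Section 10.2 calls the analysis intention to treat by randomized arm. Section 10.3.2 names a Wilcoxon rank-sum test and a mixed model for repeated measures (MMRM). Section 10 gives no rule for missing outcomes.

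**The concern.** After POD 0 there is no study treatment left to stop, so a termination at, say, POD 30 has one effect: the remaining pain, mood, quality-of-life and opioid data are not collected. Neither follow-up provision covers that case. One is tied to discontinuing the intervention, the other to a participant's own request.

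The primary endpoint is pelvic pain, and section 2.1 calls pelvic pain the most common symptom of this disease. An investigator could therefore read returning pain as disease progression. Section 8.3 offers a second possible route, because "if the study participant's condition deteriorates at any time during the study, it will be recorded as an AE". Termination could then depend on the outcome being measured. If ketamine works, more placebo than ketamine women would reach the trigger, the highest placebo scores would go missing, and the arms would look more alike at the visits that carry the long-term recovery objective. With 15 women per arm, a few such losses matter, and the scores cannot be recovered later.

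**Working it through.** **Step 1: the plan's own figure.** Section 10.4 states 80% power with 15 per arm, effect size 1.1 SD, two-sided alpha 0.05, Wilcoxon test, normal data. Simulation gives 79.5% to 80.7%, depending on the continuity correction, so the figure reproduces. It assumes 15 scores per arm at the visit tested. Loss unrelated to outcome or arm lowers it to 73% at 13 per arm, 70% at 12 and 60% at 10.

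**Step 2: illustration in VAS points.** All inputs are assumptions, because the documents give no SD, correlation or trigger: 0-10 scale with clipping, SD 2.5, within-subject correlation 0.5, placebo mean 5, ketamine mean 3.5. A woman at VAS 7 or more after POD 1 is ended with probability 0.5 at each such visit (half) or 1 (all). The rule is the same in both arms. Results are large-sample POD 83 differences, placebo minus ketamine.

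| Situation | Estimate | Half | All |
|---|---|---|---|
| Full follow-up | any | 1.41 | 1.41 |
| Pain recorded at POD 27 or 55, then ended | available scores | about 1.2 | 1.03 |
| Same | likelihood-based, as in MMRM | about 1.4 | 1.40 |
| Ended before the pain is recorded | likelihood-based | 1.19 | 0.92 |

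Relative loss: 1 - 1.03/1.41 = 27% for available scores in the second row. For the likelihood estimate in the last row, it is 1 - 1.19/1.41 = 16% to 1 - 0.92/1.41 = 35%. In the second row with all removed, 33% of placebo and 14% of ketamine women are missing at POD 83. With a placebo mean of 4 and the same 1.5-point gap before clipping, 1.34 falls to about 1.2 and to 1.07 in available scores.

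**Step 3: the same mechanism on the plan's SD scale.** True difference -1.1 SD, correlation 0.5, trigger 0.5 or 1 SD above the placebo mean, probability of being ended 0.5 or 1. Available-score differences and Wilcoxon power are at 15 per arm. The MMRM-type estimate is at 150 per arm, so that bias is visible.

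| Trigger, probability | Pain recorded first? | Missing, placebo / ketamine | Available scores | Wilcoxon power | MMRM-type |
|---|---|---|---|---|---|
| 1 SD, 0.5 | yes | 14% / 2% | -1.00 | 70% | -1.09 |
| 0.5 SD, 0.5 | yes | 27% / 5% | -0.95 | 62% | -1.09 |
| 0.5 SD, 1 | yes | 46% / 10% | -0.80 | 42% | -1.10 |
| 1 SD, 0.5 | no | 20% / 3% | -0.92 | 64% | -1.00 |
| 0.5 SD, 0.5 | no | 35% / 7% | -0.84 | 51% | -0.92 |
| 0.5 SD, 1 | no | 54% / 13% | -0.63 | 29% | -0.75 |

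**Step 4: no true effect.** With the same rule in both arms, the difference is 0.00 to -0.01 SD and the test rejects in 4% to 5% of trials. There is no bias and no inflation of the false-positive rate.

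**Step 5: how much loss the plan foresees.** Section 5.6 enrolls about 50 to keep 30, a loss of (50 - 30)/50 = 40%. Reasons are not split and some loss may precede randomization, so this does not measure investigator terminations.

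**The case against.** The list is permissive, and no passage ties termination to a VAS score. The adverse-event ground requires that staying in the study be against the woman's best interest, and phone or REDCap follow-up would rarely meet that test. The medical-condition ground applies only while she continues on study drug. Every participant enters with moderate to severe pelvic pain (section 5.1), so pain returning to that level is not clearly a deterioration under section 8.3. Follow-up staff are blinded (section 4.1). Adverse events are asked about at the visits where VAS is taken, so the pain will often be recorded before any termination, and there the planned MMRM shows essentially no bias. The trial calls itself a pilot not powered for a hypothesized VAS effect.

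Most of this stands, and it limits the point to what can happen. It does not close the gap: disease progression carries no qualifier, non-adherence is a separate ground, and neither follow-up provision reaches an investigator termination.

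A reader might infer three stronger things that the documents do not support:

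- **That the comparison is biased as planned.** Termination is discretionary and its frequency unknown.
- **That the list contradicts intention to treat.** Section 10.2 defines that by randomized arm, and missing later visits do not breach it.
- **That data of terminated women will be destroyed.** The sentence in section 5.7.2 follows one on withdrawal of consent, and the next contemplates retaining and analyzing data up to withdrawal.

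**Conclusion.** The gap is real and of moderate weight. After POD 0, a termination under section 5.7.1 can only remove POD 27 to POD 83 outcomes, and nothing in the protocol keeps those women in follow-up. If terminations track returning pain, a Wilcoxon test on available scores can understate a true benefit: 1.41 VAS points become about 1.2-1.0 in the illustration. The MMRM holds at about 1.4 when the pain is recorded first and falls to about 1.2-0.9 when it is not. The direction is attenuation. A spurious benefit would need terminations related to arm, for example through functional unblinding or ketamine-related adverse events. POD 1 is essentially unaffected.

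The sizes rest on the assumed SD, correlation, trigger and removal probability, and on reading the Wilcoxon test as using available scores, since the plan gives no missing-data rule. That the gap exists rests on the text alone.

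**What to change.** - **Section 5.7.1:** separate stopping the infusion from ending follow-up. Leave clinicians' safety and best-interest discretion over the intervention as it is. Extend the existing follow-up sentence to every randomized subject, including one whom the investigator terminates for disease progression, toxicity, an adverse event or non-adherence. With her consent, outcome collection continues to POD 83 and ends only for withdrawal of consent, death, loss to follow-up or study termination.
- **Section 5.7.2, data:** reconcile the destruction sentence with sections 5.7.1 and 13.5, so that data collected up to withdrawal are kept and analyzed.
- **Section 5.7.2, replacement:** state that a randomized subject who is replaced stays in the analysis in her assigned arm. Section 10.2 describes 30 subjects and does not say what happens to those replaced.

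The cost is protocol wording and a few more reminder calls. Section 7.2.3 already allows phone or REDCap collection at POD 27 and POD 55. Section 7.2.4 gives no mode for POD 83, so the same option should be stated there. The change reduces missing outcomes but does not supply the missing-data rule that section 10 lacks.
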